3.6 Interventions

3.6.1 Auricular Press Needle Acupuncture

Auricular Points: Heart, Kidney, Shenmen, Subcortex

① Before the application, the participants rested for 5 min, followed by baseline fMRI examination (including T1-weighted and T2-weighted images).

② After the examination, auricular press needles were inserted. The physician's hands and local acupoint areas were routinely disinfected. The experimental group used Dingshi brand disposable sterile press needles (with release paper, Medical Device Registration No.: Su Xie Zhu Zhun 20212200040, specification 0.20×1.3 mm). Disposable, sterile press needles without tips were used in the control group. The needle body was inserted at the aforementioned points, the release paper was removed, and the adhesive tape was gently pressed to ensure tight adhesion. Both ears were treated at each time-point.

③ After application, each acupoint was pressed 20 times. Pressing all eight points twice took approximately 2 min to complete. Rest for 10 min. A second pressing session was performed for 2 min. Rest for 10 min. A third pressing session was performed for 2 min, and the press needles were removed. (Total duration: approximately 26 min).

④ Immediately an fMRI examination (T2-weighted images only) was performed to observe changes in brain regions.

The intervention involved applying auricular press needles (a type of intradermal embedding needle) to specific acupoints.

[figure not shown]

Figure 1. Localization of selected auricular points.

Table 1. Common names, locations, and indications of auricular points.

Common Name	Acupuncture Point	Anatomical Location	Indications Based on TCM and Scientific Research	Mental Health and Depression Indications
Shenmen	TF4	The upper portion of the apex of the triangular fossa is closer to the upper branch of the antihelix.	Analgesic and anti inflammatory action is the most critical anesthesia point on the ear.	Sedative point. Calms the mind.
Heart	CO15	In the center of the cavum conchae	Used for cardiac complaints such as angina, cardiac rhythm disorders	Indicated for anxiety, depression, distress, mental agitation, and insomnia.
Kidney	CO10	In the cymba conchae, in a groove below the start of the inferior crus.	Used for issues in the urinary and genital systems. Assists with tinnitus, auditory conditions, and sleep disorders.	Indicated for fear, insecurity, and lack of willpower.
Subcortex	AT4	Inner and anterior faces of the antitragus	Rebalances nervous, digestive, and cardiovascular functions	Harmonizes cortical excitation and inhibition

3.6.2 ECG Patch

The ECG patch operation was divided into three stages: from the start of auricular press needle treatment to the end of the second resting-state fMRI scan.

Operation method:

①Baseline ECG data collection: After the subject rested for 5 min, the patch was attached to the corresponding chest wall position for 5 min of ECG monitoring, after which the ECG patch was removed.

②Treatment-period ECG data collection: After the baseline fMRI examination, the ECG patch was attached. Monitoring continued throughout the auricular acupuncture treatment period. The ECG patch was removed after treatment completion.

③Post-treatment ECG data collection: After the second fMRI examination, the ECG patch was attached, 5 min of ECG monitoring was performed, and then the ECG patch was removed.

The ECG data recorded by the device were transmitted to a computer or cloud, automatically analyzed using system software, or reviewed by a physician.

3.6.3 Imaging Examination

All participants underwent magnetic resonance imaging on the same day as the auricular acupuncture treatment using a Siemens Skyra 3T scanner equipped with a 16-channel head coil. The imaging protocols included conventional T1-weighted imaging (T1WI), T2-weighted imaging (T2WI), T2-fluid-attenuated inversion recovery (T2-FLAIR), high-resolution 3D-T1WI, and resting-state functional MRI (rs-fMRI). Prior to scanning, the participants were fitted with noise-canceling headphones and placed in a supine position. Head motion was minimized using foam padding. Participants were instructed to keep their eyes closed, maintain a wakeful state, and avoid engaging in any specific cognitive tasks. High-resolution T1-weighted structural scanning parameters were as follows: TR = 2300 ms, TE = 2.98 ms, FA = 9 degrees, FOV = 256 mm × 256 mm, voxel size = 1 mm × 1 mm × 1 mm, slice number = 176, thickness = 1 mm; for rs-fMRI, TR = 2160 ms, TE = 30 ms, FA = 90 degrees, FOV = 256 mm × 256 mm, matrix = 64 × 64, number of excitations (NEX) = 1, voxel size = 4 mm × 4 mm × 3 mm, thickness = 3 mm, slice gap = 0.75 mm, 40 slices, total

acquisition time = 518 s.

3.7 Observational Indicators

Resting-state functional magnetic resonance imaging was used to conduct pre- and post-intervention comparative analyses in participants receiving auricular acupuncture.

Data collection is divided into two stages:

Baseline: Collection of demographic data, baseline fMRI scan, and clinical assessment (T0).

post-intervention:fMRI scan and clinical assessment immediately after the intervention (T1).

Primary Outcome Measure

Functional connectivity strength between the insula and the medial prefrontal cortex (MPFC)(T1-T0)

This connectivity strength serves as a proxy for the efficiency of information exchange between the “interoceptive hub” and “the self-referential/emotion-regulatory hub”. An increase following auricular acupuncture may reflect enhanced psychosomatic integration and top-down emotional regulation, suggesting a functional optimization of this circuit. Conversely, a decrease could indicate a disruption of pathological hyper-connectivity related to emotional constraint or an upregulation of control—mechanisms consistent with the observed alleviation of emotional symptoms

Secondary Outcome Measures

①Local brain activity indicators:regional homogeneity (ReHo), amplitude of low-frequency fluctuation (ALFF), fractional ALFF (fALFF)(T1-T0);

ReHo captures the temporal synchrony of neural activity within local brain regions. Following auricular acupuncture, increased ReHo in regions such as the insula and prefrontal cortex may reflect improved neural coordination and functional integration. Conversely, decreased ReHo in specific areas could indicate a modulatory effect on abnormally elevated local synchrony.

ALFF reflects the intensity of spontaneous neural activity in the brain. An increase in ALFF within emotion- and cognition-related regions following auricular acupuncture may indicate an elevation in baseline neural activity or metabolic activity in these areas. Conversely, a decrease in ALFF in regions such as the limbic system could reflect an

inhibitory modulatory effect of the intervention on hyperactivity, potentially contributing to emotional stabilization.

fALFF: Changes in fALFF following the intervention allow a more specific assessment of auricular acupuncture's regulatory effects on intrinsic neural oscillations related to cognition and emotion. When interpreted in conjunction with ALFF changes, the direction of fALFF alteration can help elucidate the specific mechanisms through which auricular acupuncture modulates neural activity patterns.

②Interhemispheric coordination index: voxel-mirrored homotopic connectivity (VMHC)

The VMHC value quantifies the functional coordination between homotopic regions across the two cerebral hemispheres. Following auricular acupuncture, enhanced VMHC in regions associated with emotional regulation and cognitive control, such as the prefrontal cortex and anterior cingulate cortex, may suggest improved interhemispheric balance and integration of emotional processing. Conversely, changes in VMHC within specific regions could help clarify how the intervention modulates functional imbalances between hemispheres, particularly those related to constrained emotional states.

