3.1 Design Type

This was a parallel-group, randomized, sham-controlled clinical trial.

The study was conducted in accordance with the Consolidated Standards of Reporting Trials (CONSORT) guidelines and the Standards for Reporting Interventions guidelines. All participants provided written informed consent prior to participation and received incentives or compensation for participating in the study.

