3.3 Sample Size

The sample size estimation for functional MRI (fMRI) studies was based on Desmond's research findings. When analyzing fMRI data using a liberal threshold of 0.05, at least 12 subjects are required to achieve 80% or higher activation intensity at the single-voxel level [11]. This study randomly recruited 32 subjects, with 16 subjects per group, to systematically analyze changes in brain function before and after auricular acupuncture intervention, combined with its efficacy.

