3.8 Functional Image Processing and Statistical Analysis

3.8.1 Resting-state fMRI Data Processing

All functional imaging data were processed and analyzed using MATLAB R2022b (MathWorks) with the SPM12 toolkit, RESTplus v1.25, and DPABI v7.0 software packages. The preprocessing steps included: ①data format conversion; ②removal of the first 10 time points to eliminate unstable initial signals; ③head motion realignment and slice-timing correction. Individuals with head movements exceeding 2 mm or 2 degrees were removed; ④spatial normalization to the Montreal Neurological Institute template using the DARTEL registration algorithm, followed by resampling to an isotropic voxel size of $3\text{ mm} \times 3\text{ mm} \times 3\text{ mm}$; ⑤spatial smoothing using a 6-mm Gaussian kernel; ⑥linear detrending; ⑦regression of nuisance covariates, including 24-head motion parameters, white-matter signal, and cerebrospinal fluid signal; ⑧application of a 0.01 to 0.08 Hz bandpass filter.

Mean Regional Homogeneity (mReHo): ReHo maps were generated by calculating

Kendall's coefficient of concordance (KCC) using RESTplus V1.25 software. To minimize individual differences, the ReHo value of each voxel was normalized by dividing it by the global mean ReHo value of the entire brain, resulting in mReHo.

Mean Amplitude of Low-Frequency Fluctuation (mALFF) and its derived metric, mean fractional ALFF (mfALFF): The time series of each voxel was transformed into the frequency domain using a Fast Fourier Transform (FFT) to obtain the power spectrum. ALFF was calculated as the square root of the power spectrum. fALFF was defined as the ratio of the ALFF value in the low-frequency range (0.01–0.08 Hz) to the ALFF value across the entire frequency range (0–0.25 Hz). To minimize individual variability, the fALFF value of each voxel was normalized by dividing it by the global mean fALFF value of the whole brain, resulting in the mfALFF.

Functional images were transformed into a mirrored space after preprocessing. The mean BOLD time series for each voxel was extracted. Pearson's correlation coefficients were computed for mirrored voxels from the bilateral hemispheres to produce VMHC maps. The Fisher-z transform was used to enable subsequent group-level comparisons.

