Z-score normalized Functional Connectivity (zFC) values: Brain regions exhibiting significant between-group differences in functional metrics were defined as regions of interest (ROIs). Functional connectivity between each ROI and the entire brain was computed using the RESTplus software. The resulting correlation coefficients were subsequently standardized using Fisher's r-to-z transformation to obtain zFC values.

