3.8.2 Clinical Data

Datasets: Intent-to-Treat (ITT) and Per-Protocol (PP) analyses were used.

Normally distributed continuous data were described as mean \pm standard deviation, and inter-group comparisons for normally distributed variables used independent-samples t-tests. Non-normally distributed scale data will be described as medians and interquartile ranges, and the Mann–Whitney U non-parametric test will be used for statistical analysis. Categorical data were analyzed using the Chi-square test.

All statistical analyses were performed using SPSS or R software. Statistical significance was set at $P < 0.05$.

四、Ethics and Participant Protection

Before the study begins, the study protocol (including questionnaires and the informed consent form) will be submitted for review and approval to the Ethics Committee of Taizhou People's Hospital Affiliated to Nanjing Medical University (ethics number: LSKY 2025-175-01). Any amendments to the study protocol will be submitted to the Ethics Committee for approval and record-keeping. All participants will be fully informed about the study purpose, procedures, potential risks, and benefits, and will provide written informed consent.

五、References

- [2] de Oliveira Rodrigues DM, Menezes PR, Machado Ribeiro Silotto AE, et al. Efficacy and Safety of Auricular Acupuncture for Depression: A Randomized Clinical Trial [J]. *JAMA Netw Open.* 2023;6(11):e2345138.

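### The only connectivity rule in 3.8.1 picks seeds from observed group differences, so the primary insula-mPFC change has no fixed measure and no assigned, T0-adjusted AA-SA analysis

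*Combined protocol and SAP*

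**What the plan says.** All references are to the combined protocol and SAP.

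- **Outcome.** Section 3.7 gives the primary outcome as "Functional connectivity strength between the insula and the medial prefrontal cortex (MPFC)(T1-T0". It names no mask, coordinates, insula subregion or hemisphere.
- **Connectivity rule.** Section 3.8.1 says: "Brain regions exhibiting significant between-group differences in functional metrics were defined as regions of interest (ROIs". Each such region is then correlated with the whole brain and Fisher-transformed to zFC. No other rule for functional connectivity is given, and the section names no group-level test or threshold.
- **Tests.** Section 3.8.2, headed Clinical Data, says that "inter-group comparisons for normally distributed variables used independent-samples t-tests", with Mann-Whitney U for non-normal data. Neither test is tied to connectivity, to the change score or to T0.
- **Baseline.** The T0 stage in 3.7 is "Collection of demographic data, baseline fMRI scan, and clinical assessment (T0", so a T0 connectivity value is scheduled for every participant.
- **Design and wording.** Section 3.1 describes a "parallel-group, randomized, sham-controlled clinical trial". Section 3.7 opens with "pre- and post-intervention comparative analyses in participants receiving auricular acupuncture", and 3.3 states the aim as "to systematically analyze changes in brain function before and after auricular acupuncture intervention, combined with its efficacy". Neither of these two sentences names the AA-SA comparison.

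**The concern.** A primary outcome needs a variable that can be computed without looking at the group difference, and an analysis assigned to it. Here the variable in 3.7 and the rule in 3.8.1 do not meet. If neither the insula nor the mPFC is among the regions that differ between groups, the 3.8.1 procedure produces no primary outcome value. If one of them is, the same participants' group differences have selected the seed and are then used to test it.

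The second gap is smaller. No test is expressly attached to the primary outcome, and the tests that are named leave out the one covariate already in hand. With 16 per arm, and fewer after motion exclusions, precision is scarce.

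**Working it through.** **Step 1: does the rule in 3.8.1 deliver the outcome in 3.7?**
- Section 3.7 requires one connectivity value per scan between two named regions.
- Section 3.8.1 requires a significant between-group difference in some functional metric before a region can be a seed. Which metrics, and at what threshold, is not stated.
- The seed set is therefore unknown until group data have been compared, and nothing guarantees that it contains the insula or the mPFC.
- A later AA-SA comparison of zFC from these seeds is not independent of the selection. How far this inflates error depends on how strongly the selecting metric and zFC are related. The documents do not say, so I put no number on it.

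**Step 2: what would T0 adjustment change?**
The plan has no figure of its own to reproduce here. Inputs:
- N = 32, 16 per arm (3.3).
- Assumed, not in the documents: the T0-T1 correlation r, and the ratio k of the T1 SD to the T0 SD.
- Motion exclusions ("Individuals with head movements exceeding 2 mm or 2 degrees were removed") may reduce N. Their number is not given, so 12 per arm is used as an assumed low case.

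Formulas, with T0 SD = 1:
- Variance of the change score: 1 + k² − 2rk.
- Variance after adjusting for T0: k²(1 − r²) × [1 + 1/(N − 4)]. The bracket is the cost of estimating the slope: 29/28 = 1.036 at N = 32 and 21/20 = 1.05 at N = 24.
- The change-score variance minus k²(1 − r²) equals (1 − kr)², which is never negative. The ratio of adjusted to change-score variance therefore cannot exceed the bracket. The expected loss is at most 3.6% at 16 per arm and 5% at 12 per arm.

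With k = 1 the ratio reduces to (1 + r)/2 × 29/28:

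| r | ratio | variance reduction | equivalent n per arm (16/ratio) | CI half-width relative to change score |
|---|---|---|---|---|
| 0.3 | 0.673 | 33% | 23.8 | 0.82 |
| 0.5 | 0.777 | 22% | 20.6 | 0.88 |
| 0.7 | 0.880 | 12% | 18.2 | 0.94 |
| 0.9 | 0.984 | 2% | 16.3 | 0.99 |

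Simulation of 40,000 trials gave ratios of 0.672, 0.778, 0.879 and 0.983. Break-even is at (1 + r)/2 = 28/29, so r = 27/29 = 0.93.

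With unequal SDs:
- k = 0.8: reductions of 48%, 41% and 35% at r = 0.3, 0.5 and 0.7.
- k = 1.1: reductions of 26%, 15% and 5% at the same r; a small loss for r of about 0.79 to 0.96.
- k = 1.25: reductions of 19% and 7.5% at r = 0.3 and 0.5; a small loss for r of about 0.66 to 0.89.

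**The case against.** The strongest reply is that the plan already implies an AA-SA t-test on T1-T0. The trial is sham-controlled, 3.8.1 speaks of group-level comparisons and between-group differences, and 3.8.2 falls under the statistical analysis heading of 3.8 and names between-group tests. Much of this stands. It is a reasonable default reading, and such a test would be valid under randomisation. It does not supply a fixed insula-mPFC variable, and it does not use T0.

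A sponsor could also say that the 3.8.1 seed rule was meant as a further, exploratory analysis. That may be the intention, but the text does not say so and gives no other connectivity rule.

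It is also fair that adjustment is a choice. Its gain depends on r and k, which the documents do not give. Both scans fall on the same day (3.6.3), so a high r, where little is gained, cannot be ruled out.

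Three stronger readings are tempting but unsupported:
- **That the plan intends, or leaves open, a pre/post test in AA alone as the primary analysis.** No within-arm test is named anywhere, and the continuous-data tests that are named are between-group. The before/after sentence in 3.3 follows directly from the count of 16 in each group, so it need not mean AA only. The fault is loose wording.
- **That a T1-only comparison is still open.** The outcome is defined as T1-T0, which excludes it.
- **That the change score is biased, or that adjustment always wins.** Neither is true, as the working shows.

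**Conclusion.** The point holds on two parts. First, the connectivity rule in 3.8.1 contradicts the a-priori pair in 3.7: it may produce no primary outcome value, and any group comparison resting on it is circular. This is the weightier part and needs no assumptions. Second, no analysis is expressly assigned to the primary outcome, and the tests available are unadjusted although T0 is collected. With equal SDs and 16 per arm, adjustment would cut the variance by about 33% to 2% over assumed correlations of 0.3 to 0.9. The worst expected loss is 3.6%, or 5% at 12 per arm. That part concerns precision and chance T0 imbalance, not validity. The pre/post phrasing in 3.3 and 3.7 should be aligned with the sham-controlled design as a matter of wording.

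**What to change.** Add a short paragraph to 3.8 along these lines:

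> The primary analysis is the AA-SA difference in the T1-T0 change in Fisher-z connectivity between one insula ROI and one mPFC ROI. Masks and hemisphere handling are fixed before unblinding and are not chosen from between-group differences. The difference is estimated by regression of T1-T0 on arm and T0, and reported with its 95% CI. Within-arm pre/post tests are descriptive. Connectivity of seeds selected from between-group differences is exploratory.

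Regressing T1 on arm and T0 gives the same arm effect, so the outcome definition in 3.7 can stand. The same paragraph should state the atlas or coordinates, that the test is two-sided, how motion exclusions fit with the ITT set, and whether Mann-Whitney U is kept only as a sensitivity analysis. Reword the pre/post sentences in 3.3 and 3.7 to name the AA-SA contrast.

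If the sponsor prefers an unadjusted AA-SA test of T1-T0, that is acceptable provided that it is named and the ROIs are fixed.

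Cost: a paragraph and two reworded sentences, with no new data. Adjustment uses one residual degree of freedom (29 instead of 30). It loses a little precision, within the limits given above, when the correlation is very high or the T1 SD is larger than the T0 SD.

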Resting-state functional magnetic resonance imaging (rs-fMRI) provides a key tool for investigating the modulation effects of Vagus Nerve Stimulation (VNS) on brain functional connectivity (FC) by measuring the blood-oxygen-level-dependent (BOLD) signal arising from spontaneous neural activity in the absence of tasks. Functional connectivity (FC), which refers to temporal correlations in spontaneous neural activity between distinct brain regions, is known to be aberrant in various neurological disorders [8-9]. Specific studies have demonstrated that aVNS can significantly modulate FC in multiple brain networks. Studies have indicated that aVNS attenuates negative FC between the insula and the medial prefrontal cortex (mPFC), a mechanism that may enhance the balance between interoceptive awareness and cognitive experience [1]. In patients with primary insomnia, rs-fMRI analyses revealed that taVNS reduced FC between the mPFC and dorsal anterior cingulate cortex (dACC, part of the salience network), as well as between the mPFC and occipital cortex. This reduction in FC was positively correlated with improvements in the Pittsburgh Sleep Quality Index (PSQI) scores, suggesting that taVNS may improve sleep by modulating interactions between the default mode network (DMN), salience network, and the visual cortex [8]. Furthermore, in migraine research, repeated taVNS treatment modulated resting-state FC (rsFC) between brainstem areas (e.g., NTS, RN), the limbic system (bilateral hippocampus), pain-processing regions (bilateral postcentral gyri, thalamus, and mPFC), and basal ganglia (putamen/caudate). Notably, changes in rsFC between the RN and putamen were significantly correlated with a reduction in monthly migraine days, underscoring the role of taVNS in pain modulation pathways [9]. Another study on primary insomnia found that taVNS reduced FC between the basal forebrain (BF) and the visual cortex (e.g., middle occipital gyrus, fusiform gyrus), sensorimotor cortex (supplementary motor area), and mPFC. Weakening of the connection between the basal forebrain and middle occipital gyrus was associated with improvements in the Insomnia Severity Index (ISI). More importantly, baseline FC within the basal-forebrain–visual circuit predicts therapeutic response to taVNS, supporting its potential

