3.4 Study Population and Criteria

Study Subjects

Inclusion Criteria:

- (1) Age 18–30 years;
- (2) Basically normal diet and sleep;
- (3) No history of mental illness;
- (4) No MRI contraindications (e.g., metal implants or pacemakers) or claustrophobia;
- (5) Willing to participate in this study and sign the informed consent form.

Exclusion Criteria:

- (1) Presence of auricular skin lesions or allergy to adhesive ear patches;
- (2) Currently receiving regular acupuncture treatment;
- (3) History of bleeding disorders or anticoagulant use (increased bleeding risk);
- (4) Previous history of syncope during acupuncture.

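### Section 3.7 reads both an increase and a decrease in the primary outcome favourably, without defining its sign, so a change opposite to taVNS could be presented as support

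*Combined protocol and SAP*

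**What the plan says.** The primary outcome in section 3.7 is the T1−T0 change in FC strength between the insula and the mPFC. An increase is read this way: "An increase following auricular acupuncture may reflect enhanced psychosomatic integration and top-down emotional regulation, suggesting a functional optimization of this circuit". The next sentence reads the other direction: "Conversely, a decrease could indicate a disruption of pathological hyper-connectivity related to emotional constraint or an upregulation of control", and calls these "mechanisms consistent with the observed alleviation of emotional symptoms".

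ReHo, a secondary outcome in the same section, has a similar pair. For a rise: "increased ReHo in regions such as the insula and prefrontal cortex may reflect improved neural coordination and functional integration". For a fall: "Conversely, decreased ReHo in specific areas could indicate a modulatory effect on abnormally elevated local synchrony".

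The primary objective (Study Objectives) is to find out whether auricular acupuncture can modulate this connection in the way taVNS does. The introduction gives the taVNS effect a direction: "Studies have indicated that aVNS attenuates negative FC between the insula and the medial prefrontal cortex (mPFC"), and repeats it when setting out the rationale.

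Section 3.2 recruits healthy adults, and section 3.4 requires "No history of mental illness". Section 3.8.2 sets significance at P < 0.05 without saying whether tests are one- or two-sided. No section names the sign of the between-group difference that would count for or against the objective.

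**The concern.** An outcome can answer a question only if some result would count against the proposed answer. The objective here asks about similarity to an effect whose direction the plan itself reports. One direction of change is therefore like taVNS and the other is not. Section 3.7 does not draw that line; it provides a benefit for each side.

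Two supports for the favourable reading of a decrease are also weak within this plan. One is an abnormal baseline state that the eligibility criteria give no reason to expect. The other is emotional relief, for which the plan lists no outcome. If the trial found a clear change away from the taVNS pattern, the authors could cite their own protocol for calling it beneficial, and a reader would have no prespecified rule to set against that.

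**Working it through.** The point rests on no figure in the plan, so there is none to reproduce. The check is to set the statements side by side.

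**1. Does each direction have a favourable reading?**

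| Outcome | Increase | Decrease | Both favourable? |
|---|---|---|---|
| Insula–mPFC FC (primary) | Circuit optimised, better regulation | Pathological state disrupted or control upregulated, linked to symptom relief | Yes |
| ReHo | Better coordination and integration (insula, prefrontal cortex) | Acts on abnormally high synchrony (areas not named) | Yes, less clearly: the fall is favourable only by implication, and the regions differ |
| ALFF | More baseline or metabolic activity; no benefit named | Dampened hyperactivity, possible emotional stabilisation | No |
| fALFF | No benefit attached | No benefit attached | No |
| VMHC | Better interhemispheric balance | Decrease not addressed; changes may clarify imbalance | No |

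**2. Which direction is taVNS-like?** Take FC negative at baseline, as the description of taVNS presupposes.

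| Definition of strength | taVNS-like change (toward zero) | Opposite change (further from zero) | Reading of the opposite change in 3.7 |
|---|---|---|---|
| Signed FC | Increase | Decrease | Favourable |
| Absolute FC | Decrease | Increase | Favourable |

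Section 3.7 does not choose between the definitions. Section 3.8.1 applies Fisher's r-to-z transformation, which keeps the sign, but describes it for regions selected because they differ between groups. It does not say that the primary outcome is that signed value. Under either definition the opposite change receives a favourable reading, so the concern does not depend on the choice.

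If FC is not negative at baseline in these volunteers, a rise in signed FC is not an attenuation of negative FC at all. The plan gives no baseline sign for this population, so a rule must cover that case.

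**3. Does the population fit the decrease readings?** Participants are healthy, aged 18–30, with no history of mental illness. The plan offers no ground for expecting pathological connectivity or abnormally high local synchrony in them. The alternative in the primary-outcome sentence, upregulated control, does not need an abnormal baseline.

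**4. Is the emotional benefit measured?** The listed outcomes are FC, ReHo, ALFF, fALFF and VMHC. Section 3.7 also schedules a clinical assessment at T0 and T1, section 3.8.2 refers to scale data, and the ethics section mentions questionnaires. No instrument is named, and no emotional measure is an outcome.

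**The case against.** The strongest reply is that these sentences are explanatory prose, hedged throughout with may and could. They set no success criterion and no reporting rule. The objective already asks for similarity to taVNS, so an opposite change would fail it on its own terms. The objective is also framed as a question about modulation, not as a directional hypothesis. All of this is correct, and it limits the point: the plan permits a favourable account of an opposite result but does not require one. It does not remove the point, because the plan contains no other rule and the objective's direction is left to inference.

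Four stronger readings are tempting and are not supported.

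- A reader might infer that an opposite result would be reported as support, or that no result could contradict the plan. That is a prediction; the documents show only that nothing prevents it.
- A reader might extend the point to ALFF because of the sentence beginning "Conversely, a decrease in ALFF in regions such as the limbic system could reflect". Only that decrease is tied to a benefit. The increase is described neutrally, and the two concern differently described regions.
- A reader might infer an inflated error rate: 5% rather than 2.5% under no effect, or 1 − 0.95^5 = 22.6% over five outcomes. The first contrast is simply a two-sided test against one of its tails, and the fix keeps the same test. The second is a multiplicity figure that assumes five independent tests and includes outcomes without two favourable readings. Likewise, 80% power for a wrong-way effect of 1.02 SD with 16 per arm is a property of any two-sided trial of this size. None of these measures the problem.
- A reader might conclude that all secondary outcomes should become descriptive. That does not follow from a fault in interpretation.

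**Conclusion.** The concern holds for the primary outcome and, less clearly, for ReHo. Both directions have a favourable reading. The decrease readings lean on abnormal states that the plan gives no reason to expect in healthy adults and, for the primary outcome, also on emotional relief for which no outcome is listed. A change opposite to the taVNS effect could therefore be presented as support.

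The size is qualitative. It affects what the one primary comparison can be said to show, not its type I error, power or estimate. The conclusion rests on taking the comparison with taVNS to imply a direction, which the introduction supports but no hypothesis states. It does not depend on whether FC strength is signed or absolute. The plan should be changed, since the correction is cheap and decides what the trial can conclude.

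**What to change.** In section 3.7:

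1. Define the primary outcome as signed Fisher-z insula–mPFC FC, and report its baseline mean and sign.
2. Add a rule such as: *The AA−SA difference in T1−T0 change will be tested two-sided at 0.05. Only a difference that moves negative FC toward zero (AA−SA > 0 when baseline FC is negative) supports a taVNS-like effect. A significant difference in the other direction will be reported as not supporting it. If baseline FC is not negative, the result will not be described as attenuation of negative FC.*
3. Delete the readings that assume pathological connectivity or abnormally elevated synchrony, and the reference to symptom relief as already observed.

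The secondary outcomes can keep their present status.

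The change is to wording only and needs no further participants or data. The downside is that an effect opposite to taVNS can no longer be presented as positive.
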